4.3 Exclusion Criteria

Disease Related

- Disease-associated symptoms requiring immediate therapy or other interventions
- Known brain metastases or cranial epidural disease unless adequately treated with radiotherapy and/or surgery and stable for at least 3 months before planned first dose of study drug

Laboratory

- Absolute neutrophil count < $1.5 \times 10^9/L$
- Platelet count < $100 \times 10^9/L$
- Hemoglobin < 9 g/dL
- Bilirubin > 1.5 X upper limit of normal (ULN)
- Aspartate aminotransferase (AST) or alanine aminotransferase (ALT) > 2.5 X ULN (OR > 5 X ULN in the presence of known liver metastases)
- Serum creatinine > 1.5 X ULN OR estimated creatinine clearance ≤ 60 ml/min (Cockcroft-Gault)
- Partial thromboplastin time (PTT) > 1.25 X ULN
- Prothrombin time (PT) > 1.25 X ULN OR international normalization ratio (INR) > 1.4

Medications

- Radiation therapy for bone metastasis within 2 weeks, any other external radiation therapy within 4 weeks before planned first dose of study drug. Systemic treatment with radionuclides within 6 weeks before planned first dose of study drug. Subjects with clinically relevant ongoing complications from prior radiation therapy are not eligible
- Prior treatment with everolimus, or any other specific or selective TORC1/PI3K/AKT inhibitor (e.g., temsirolimus)
- Receipt of any type of small molecule kinase inhibitor (including investigational kinase inhibitor) within 2 weeks before planned first dose of study drug
- Receipt of any type of anticancer antibody (including investigational antibody) within 4 weeks before planned first dose of study drug
- Taking strong inducers or inhibitors of CYP450s for subjects receiving everolimus
- Chronic treatment with corticosteroids or other immunosuppressive agents
- Concomitant anticoagulation at therapeutic doses with oral anticoagulants or platelet inhibitors
- Subjects with a known hypersensitivity to everolimus or other rapamycins (sirolimus, temsirolimus) or to its excipients
- Not recovered from toxicities related to any prior treatments, unless adverse events are clinically non-significant and/or stable on supportive therapy

General

- History of any medical, psychiatric, or social (e.g., addictive disorder) conditions, or laboratory abnormality that in the opinion of the investigator, may increase the risks associated with study participation or treatments that may interfere with the conduct of the study or the interpretation of study results

- Major surgery within 2 months before planned first dose of study drug. Complete wound healing from major surgery must have occurred within 1 month before planned first dose of study drug and from minor surgery at least 10 days before planned first dose of study drug
- Myocardial infarction within the previous 6 months before planned first dose of study drug
- Active infection requiring parenteral antibiotics within 2 weeks before planned first dose of study drug
- Diagnosis of another malignancy within 2 years before planned first dose of study drug, except for superficial skin cancers, or localized, low grade tumors;
- Currently enrolled in and has not yet completed at least 30 days since ending other investigational device or drug study before planned first dose of study drug, or subject is currently receiving other investigational agent(s).
- Prior or current history of hepatitis B, hepatitis C or human immunodeficiency virus
- Pregnant, planning a pregnancy or breastfeeding during the study
- Sexually active fertile subjects (male and female), must agree to use medically accepted methods of contraception during the course of the study and for 30 days after the last dose of study treatment. Female subjects must meet at least one of the following criteria:
 - be surgically sterile (i.e., have had bilateral tubal ligation, hysterectomy, or bilateral oophorectomy at least 6 months before enrollment; appropriate documentation will be required),
 - be post-menopausal for at least 12 months OR
 - if sexually active, be willing to use double-barrier contraception (e.g., condom with spermicide), intrauterine device, steroidal contraceptive (oral, transdermal, implanted, or injected) or other method, approved by the sponsor.
- Unwilling or unable to comply with study requirements or not available for follow-up assessments
- Any other major illnesses that in the investigator's judgment substantially increases the risk associated with the subject's participation in the study

5. SUBJECT ENROLLMENT

5.1 Subject Recruitment

Subjects will be enrolled from the cancer populations being followed at the investigational sites. The site personnel will discuss the possibility of participation directly with subjects being seen in the center who may be appropriate candidates for the study. A description of the protocol will be posted on the www.clinicaltrials.gov website.

5.2 Subject Registration

Before subjects may be entered into the study, Rexahn requires a copy of the site's written institutional review board (IRB) approval of the protocol, informed consent form, and all other subject information and/or recruitment material, if applicable (see Section 11.3). A subject must

personally sign and date the consent form before any study specific screening assessments are done. Procedures that are performed as standard of care may be used for screening provided they are still within the 14 day screening period unless otherwise indicated.

After a subject has completed the necessary screening assessments, any questions regarding the eligibility of a subject should be discussed with the study sponsor before enrollment/randomization of the subject into the study. A subject will be considered enrolled or randomized when they are determined eligible and receive their treatment assignment.

The study sponsor or its designee will assign each subject a unique subject identification number (a 2-digit site number followed by a 3-digit subject number). The subject number must be used for subject identification on all study-related documents (e.g., electronic case report forms (eCRFs), clinic notes, laboratory samples, CT scans, MRIs, etc.). In order to obtain a subject number, the site must provide completed eligibility documents to the sponsor or designee who will provide confirmation of eligibility by either fax or e-mail to the site. Of note, subjects may be rescreened for laboratory values not meeting the criteria only once for study eligibility. A subject will be considered enrolled or randomized when the treatment has been assigned.

5.3 Subject Enrollment/ Randomization and Treatment Assignment

Subjects in Stage 1 will be enrolled to receive the combination everolimus with escalating doses of RX-0201. Subjects in Stage 2 will no longer be randomized to 1 of 2 treatment arms (i.e., everolimus versus everolimus/RX-0201). All subjects in Stage 2 will now be assigned to the everolimus/ RX-0201 treatment arm.

The site will provide documentation showing that the subject meets the eligibility requirements. Following a review of supporting documentation, by the sponsor or its designee, the site will receive the treatment assignment and a confirmation of enrollment/randomization. Subjects should be dosed within 5 days of enrollment/randomization.

5.4 Subject Replacement

Subjects in Stage 1 who are enrolled but not treated and subjects who discontinue treatment before completion of Cycle 1 for reasons other than the occurrence of a DLT may be replaced. Any replacement subject will be enrolled into the same dosing group as that for the subject who withdrew.

Subjects in Stage 2 who are enrolled but not treated will be replaced.

6. TREATMENT PROCEDURES

The only investigational product in this study will be RX-0201. RX-0201 will be administered in combination with everolimus. Everolimus will not be provided by the sponsor.

6.1 Study Drug Administration

6.1.1 Everolimus Dose Administration

Subjects will take 10 mg of everolimus orally, once daily at approximately the same time every day, consistently either with or without food. Everolimus should be swallowed whole with approximately 8-10 ounces of water.

If a subject misses a dose of everolimus, they may still take it up to 6 hours after the time they would normally have taken it. If more than 6 hours have elapsed, they should be instructed to skip the dose for that day. The next day, they should take everolimus at the usual time.

Subjects should not take 2 doses to make up for the one dose that they missed.

Drug compliance should be recorded in the subject's medical record and in the eCRF. This information will include amount of everolimus that should have been taken over a given time interval and the amount actually taken by the subject. (Section 10.3)

6.1.2 RX-0201 Dosing Schedule

RX-0201 will be administered on a cyclical basis. For subjects assigned to receive RX-0201 and everolimus, a cycle will be defined as the period elapsing from the first day of RX-0201 administration through Day 21 of the cycle or to the recovery from any adverse events sufficient that a new cycle of therapy can be administered (e.g., on Day 29 or Day 36), whichever occurs later. Once a new cycle starts, the prior cycle is considered to be completed. For subjects assigned to the everolimus only arm, a cycle will be defined as the period elapsing from the first day of everolimus administration through Day 21 of the cycle or to the recovery from any adverse events sufficient that a new cycle of therapy can be administered, whichever occurs later.

6.1.3 RX-0201 Dose Administration

The dose of RX-0201 will be based upon the subject's actual weight measured on the morning of the planned dosing. The body surface area will be calculated using the Dubois or Mosteller formulas; the same formula must be used for the subject throughout the study. All body surface area and dosing calculations will be documented in the subject's medical record and eCRF, if applicable. The starting dose of RX-0201 will be 125 mg/m²/day. This dose will be administered to eligible subjects in a 24 hour continuous intravenous infusion for 2 weeks followed by 1 week of rest in each 21 day cycle.

For each RX-0201 treatment cycle, a total of two 1000 ml infusion bags containing RX-0201 will be used. Each infusion bag will be prepared immediately before use and will contain enough RX-0201 for 7 days plus 10% overage (or overage acceptable by institutional practices) of infusion (see Appendix D for details). The first bag will be prepared on Day 1 of each 21 day cycle. The second bag will be prepared on Day 8 of each 21 day cycle. Day 15 will be the start of the 1 week rest period.

RX-0201 will be administered via continuous infusion using an ambulatory infusion pump through a vein in the arm or a indwelling catheter (i.e. Port-a-Cath® or PICC line).

RX-0201 should not be mixed with or administered as an infusion simultaneously with other medicinal products. The indwelling infusion line should be flushed with saline before and after the investigational product administration to avoid mixing with other drug products or intravenous solutions. Pharmacokinetic samples should be obtained in the opposite arm.

The date, time (i.e., start and stop) and volume infused (i.e., either initial and remaining volumes or volume infused off the pump) will be recorded in the subject's medical record and eCRF, if applicable.

6.2 Rationale for the RX-0201 Dose and Dosing Interval

The RX-0201 dosing schedule was selected on the basis of results from a first in human Phase 1 single agent study (RX-0201-P1-A-03) and a Phase 2 RX-0201 combination with gemcitabine study in pancreatic cancer (RX-0201-P2-A-07). Because there is no clinical data available using RX-0201 in combination with everolimus, Stage 1 of the study will assess the safety of RX-0201 in combination with everolimus.

6.3 RX-0201 Dose Limiting Toxicity

Initially 3 subjects will be enrolled to receive everolimus plus 125 mg/m²/day of RX-0201. If there are any dose limiting toxicities (DLTs) attributed to RX-0201 the following dose-escalation decisions will be followed:

Table 1: Phase 1 RX-0201 Dose Escalation		
Dose Group	Theoretical dose(mg/m²/day)	Escalation
1	125	-
2	200	1.60
3	250	1.25

The following dose-escalation rules will be employed:

- If 0 of the first 3 subjects experience DLT during the first 3 weeks of treatment, then the dose will be escalated to the next higher level in 3 subsequent subjects.
- If 1 of the first 3 subjects experiences DLT at the current dose during the first 3 weeks of treatment, then 3 more subjects will be accrued at the same dose level.
- If 0 of the 3 additional subjects experience DLT during the first 3 weeks of treatment, then the dose will be escalated to the next higher level in 3 subsequent subjects.
- If ≥ 1 of the 3 additional subjects in a cohort experiences DLT in the first 3 weeks of treatment, the MTD has been exceeded and 3 more subjects will be treated at the next lower dose level (if only 3 subjects were previously treated at that prior dose level).
- If ≥ 2 of 3 or ≥ 2 of 6 subjects experience DLT during the first 3 weeks of treatment, then the MTD has been exceeded and 3 more subjects will be treated at the next lower dose level (if only 3 subjects were previously treated at that prior dose level).
- Each group of 3 subjects within a cohort must be observed for a minimum period of 3 weeks without DLT before subsequent subjects are enrolled at the next higher dose level.
- Escalation to the next dose level of the study can occur upon review of the safety data from all ongoing and previous subjects and with the concurrence of the study sponsor and the principal investigators.

In the event that attribution of causality of potential DLTs to study drug may be equivocal, discussions with the investigators, medical monitor and sponsor will occur and additional subjects may be enrolled at that dose level. Reviews will be conducted by the investigators, medical monitor and sponsor of all available safety data on an ongoing basis throughout the study. The study sponsor or its designee will notify the sites when enrollment into a dose level is complete and when the next dose level is open to enrollment during Stage 1.

6.4 Determination of MTD or the RX-0201 Recommended Stage 2 Starting Dose

The establishment of the MTD or the safety of the target RX-0201 dose of 250 mg/m²/day will be based on a review of the overall safety data by the investigators, medical monitor and sponsor. The MTD is the highest starting dose level associated with first-cycle DLTs in < 33.3% of subjects. Once the safety of the MTD of the target RX-0201 dose of 250 mg/m²/day is initially established, additional subjects (up to 20 subjects total) will be enrolled to receive the target RX-0201 dose of 250 mg/m²/day in Stage 2. Selection of a recommended Stage 2 starting dose

from within the tested dose range will be based on evaluation of available safety information with findings regarding compliance, and achievement of targeted pharmacokinetic values.

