9.3 Sample Size Considerations

Approximately 9 subjects will be enrolled in Stage 1 of the study. Stage 1 is designed to determine the MTD up to a target dose of 250 mg/m²/day of RX-0201, thus the sample size for the study is not based on a formal statistical hypothesis but will be determined based on observed number of first-cycle DLTs at each dose level. The sequential 3+3 dose-escalation is

consistent with usual oncologic paradigms for dose ranging as the intent is to limit the number of subjects who are exposed to toxic doses of the treatment combination. The trial will use the standard National Cancer Institute (NCI) definition of MTD (starting dose associated with DLT in < 33.3% of subjects during the first cycle of therapy).

The planned sample size for Stage 2 is approximately 10 subjects in the everolimus arm and 20 subjects in the everolimus/ RX-0201 arm. The primary goal is to provide preliminary estimates of safety and efficacy endpoints when combining everolimus and RX-0201. Safety endpoints will be reported as described in Section 8. The primary efficacy endpoint is progression free survival estimated using the Kaplan-Meier method and associated 90% confidence intervals. Median PFS is expected to be 4.5 months in the everolimus only arm and 9 months in the combination arm. With 10 evaluable subjects in the everolimus only arm the width of the two-sided 90% confidence interval for 9-month PFS will be no more than ± 0.28 . With 20 evaluable subjects in the combination arm the width of the two-sided 90% confidence interval for 9-month PFS will be no more than ± 0.20 .

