### **7.2.4 Dose Limiting Toxicity Analysis Set**

The dose limiting toxicity assessment set will include all evaluable subjects. An evaluable subject is any subject who experiences a dose limiting toxicity in the first 21 days of treatment or completes 2 weeks of RX-0201 treatment in cycle 1.

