## Safety Analyses

The incidence of subjects with adverse events and clinical laboratory abnormalities, defined as dose limiting toxicities after 1 cycle of therapy, is one of the primary endpoints. The safety of RX-0201 will be evaluated through reporting using the grading system in the CTCAE version 4.03 for adverse events and laboratory abnormalities. This will be used to grade changes in vital signs, and laboratory assessments to include serum chemistry, hematology, coagulation tests and urinalysis. All statistical methods for safety data will be descriptive in nature.

Dose Limiting Toxicities that occur during Cycle 1 will be tabulated by DLT criteria and RX-0201 dose level. Vital signs will be tabulated and presented as raw data and change from baseline at each time point. Laboratory safety data will be tabulated in shift tables based on laboratory-specific normal ranges. Adverse events will be tabulated by body system, intensity and relationship to study drug.

Vital signs, weight, and data will be summarized using appropriate descriptive statistics, by treatment group and time.

All subjects who receive at least 1 dose of RX-0201 will be included in the final summaries and listings of safety data. All safety analyses will be performed by dose level, treatment cycle, and week, where appropriate.

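### Stage 1 states two DLT windows, three weeks and Cycle 1, and they differ for any subject whose Cycle 1 is extended for toxicity

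*Protocol*

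**What the plan says.** Three weeks or 21 days:

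- Protocol 6.3, repeated in SAP 5.5.2, words its escalation rules by weeks: "If 0 of the first 3 subjects experience DLT during the first 3 weeks of treatment". Each group of three "must be observed for a minimum period of 3 weeks without DLT before subsequent subjects are enrolled at the next higher dose level".
- SAP 7.2.4 defines the evaluable subject as "any subject who experiences a dose limiting toxicity in the first 21 days of treatment or completes 2 weeks of RX-0201 treatment in cycle 1".

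First cycle or Cycle 1:

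- Protocol 6.4 defines the MTD: "The MTD is the highest starting dose level associated with first-cycle DLTs in < 33.3% of subjects". SAP 5.5.3 and 7.3.3 repeat it. Protocol 9.3 has the same criterion: "starting dose associated with DLT in < 33.3% of subjects during the first cycle of therapy".
- SAP 4.3 and 5.5.1 evaluate DLTs during Cycle 1.
- The SAP Safety Analyses section says: "Dose Limiting Toxicities that occur during Cycle 1 will be tabulated by DLT criteria and RX-0201 dose level".
- After the three-week rules, SAP 5.5.2 adds a sentence resting the escalation decision on Cycle 1 DLTs in at least three subjects.

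Length of a cycle: Protocol 6.1.2, repeated in SAP 5.1, ends a cycle at the later of Day 21 and "recovery from any adverse events sufficient that a new cycle of therapy can be administered (e.g., on Day 29 or Day 36"). Protocol 6.6.2 delays the next cycle week by week, with no stated limit.

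The DLT criteria in Protocol 6.5 and the Stage 1 endpoint in Protocol 9.2.1.1 carry no time window.

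**The concern.** DLT incidence is the Stage 1 primary endpoint, and the Stage 2 dose rests on Stage 1. A DLT rate needs one observation window, the same for the events counted and the subjects counted.

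Here the longer window opens only for subjects whose toxicity has not recovered in time for the next cycle, so the length of follow-up depends on the outcome being measured. A first qualifying event after Day 21 in such a subject counts in the SAP's Cycle 1 table and in the MTD rate, but not under the three-week rules. Two analysts following the documents could report different DLT counts from the same data.

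The analysis set adds a second mismatch. A subject whose first DLT falls after Day 21, and who did not complete two weeks of RX-0201, has a Cycle 1 DLT but meets neither limb of SAP 7.2.4. Protocol 9.5.2.1 ties the DLT summary to that set. The event would then be in the numerator and the subject outside the denominator.

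**Working it through.** **Inputs.** Stage 1 size of about 9 and the < 33.3% limit (Protocol 9.3); three dose levels in cohorts of three (6.3); subjects treated, 3, 4 and 3 at 125, 200 and 250 mg/m²/day (2.3.2); example restart days 29 and 36 (6.1.2).

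**1. The plan's own figures.** 3 levels × 3 subjects = 9, as stated. When the two windows coincide, the limit agrees with the escalation rules: 0/3 = 0%, 0/6 = 0% and 1/6 = 16.7% meet it; 1/3 = 33.3% and 2/6 = 33.3% do not.

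**2. Difference between the windows.** If Days 29 and 36 are the first days of Cycle 2, Cycle 1 ends on Day 28 or Day 35. That is 28 − 21 = 7 or 35 − 21 = 14 days longer; 7/21 = 33% and 14/21 = 67% of the 21-day window. For a subject who is not delayed the difference is zero.

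**3. Effect of one first DLT after Day 21 in an extended Cycle 1.**

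| Cohort | Days 1–21 | Cycle 1 | Meets < 33.3% under Cycle 1? |
|---|---|---|---|
| 3 subjects, no earlier DLT | 0/3 = 0% | 1/3 = 33.3% | No |
| 4 subjects, no earlier DLT | 0/4 = 0% | 1/4 = 25% | Yes |
| 6 subjects, one earlier DLT | 1/6 = 16.7% | 2/6 = 33.3% | No |

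The first row fits the 125 and 250 levels and the second fits 200. No cohort reached six, so the third row is hypothetical. These rates use treated subjects as the denominator. The fourth subject at 200 is not explained; if one of the four were not evaluable, the rate there would be 1/3.

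**4. How often this could happen.** The documents give no rate, so this is a range on assumptions. Let q be the chance that a subject without a DLT by Day 21 has a first DLT later in an extended Cycle 1. For three such subjects, P(at least one) = 1 − (1 − q)³:

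- q = 2%: 1 − 0.98³ = 5.9%
- q = 5%: 1 − 0.95³ = 14.3%
- q = 10%: 1 − 0.90³ = 27.1%

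Let p be the chance of a DLT by Day 21. The 3+3 chance of escalating at one level is (1 − p)³ + 3p(1 − p)⁵. Under the Cycle 1 window, p is replaced by p + (1 − p)q. For p = 20% this gives 0.512 + 0.197 = 70.9% with 21 days. With Cycle 1 it gives 67.4%, 62.2% and 53.6% for q = 2%, 5% and 10%. For p = 10% it is 90.6% against 87.5%, 82.4% and 73.0%.

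**5. Search for a rule that settles it.** Neither document fixes Cycle 1 at 21 days for DLT purposes or says which window takes precedence. SAP 4.3 has the data capture system flag DLTs, but does not say which window the flag uses. SAP 11 records no changes to the protocol.

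**The case against.** The best defence is that the authors meant the same thing by both terms. The schedule is described throughout as a 21-day cycle, and SAP 5.5.2 puts the two wordings side by side as if interchangeable. For subjects who start Cycle 2 on time they are interchangeable. But the cycle definition expressly departs from 21 days, so intent cannot be relied on for a delayed subject.

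Other parts of the defence stand and limit the point:

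- Escalation is not tied to three weeks alone. SAP 5.5.2 also ties it to Cycle 1, so it is not established that a late event would be disregarded for escalation.
- Protocol 6.3 and 6.4 call for review of all safety data, so a late event would be open to judgement under either label. That review does not define the count in the primary endpoint table.
- One DLT in three leads, under Protocol 6.3, to three more subjects, not to a failed dose.
- SAP 7.2.4 defines who is evaluable, not which events count, and completing two weeks of RX-0201 is the usual way in. The denominator problem needs a late DLT in a subject who did not complete them.
- Day 29 and Day 36 are examples and apply to delayed cycles, not to every subject with toxicity.

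A reader might also infer that the window decides whether laboratory DLTs can be seen at all, because the next scheduled panel belongs to Cycle 2 Day 1. The documents do not support that. Protocol Appendix A allows the panel up to 3 days before Day 1, so one taken for a planned Day 22 start can fall on Days 19 to 21. Protocol 6.6.1 also permits more frequent laboratory monitoring.

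**Conclusion.** The inconsistency is real and stands in the current text of both documents. It affects only subjects whose Cycle 1 is extended, and it matters only if a first RX-0201-related DLT falls after Day 21 in such a subject. In a cohort of three, one such event is enough to separate the two readings of the MTD criterion; in a cohort of four it is not.

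A reader might infer that Stage 1 produced two different answers, or that the 250 mg/m²/day conclusion is unsafe. The documents do not show either. Protocol 2.3.2 reports Stage 1 as complete with no cohort of six, which is consistent with no cohort having triggered expansion but does not prove it. It puts 81% of events at mild or moderate, leaving 100 − 81 = 19% above that, without timing or DLT status. It bases the recommended dose on tolerability and does not report an MTD. A late DLT can be neither shown nor excluded. The percentages in step 4 of the working rest on assumed p and q and describe the plan, not the observed data.

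The point is still worth acting on: it concerns the count behind a primary endpoint, and resolving it costs very little.

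**What to change.** The sponsor should reconcile Protocol 6.1.2, 6.3, 6.4 and 9.3 with SAP 4.3, 5.1, 5.5.1, 5.5.2, 5.5.3, 7.2.4, 7.3.3 and the Safety Analyses section. One stated window should apply to the events counted, the subjects counted and the MTD criterion, and the text should say which passage governs. Which window to adopt is for the sponsor to decide.

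Because Stage 1 is complete, the SAP's DLT table should:

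- give the onset day of each qualifying event;
- show the count and rate by dose level both for Days 1 to 21 and to the end of each subject's actual Cycle 1;
- use a denominator that includes every subject with a counted event;
- state whether the conclusion at 250 mg/m²/day is the same under both.

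The cost is one extra table column and wording changes in the SAP and the protocol. Adverse event start dates are already recorded (Protocol 8.3), so no new data are needed.
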